## **Recruitment and Participant Population:**

**Recruitment:** Participants will be recruited through, a) media advertisements (such as Craigslist and facebook), b) using Trialfacts, a professional recruitment agency (similar to our last trial), and c) via referrals from addictions medicine clinics. Ads will recruit heavy cannabis users who are interested in quitting or substantially reducing their use of cannabis. Participants will undergo a phone screen to ensure they meet basic eligibility criteria (see included phone screen), and those who do will be invited for a full screening visit.

## **Participant Population:**

**Inclusion Criteria: 1)** Participants must be able to provide informed consent and function at an intellectual level sufficient to allow accurate completion of all assessment instruments. **2)** Participants must be between the ages of 18 and 65. **3)** Participants must meet DSM-5 criteria for at least moderate Cannabis Use Disorder, with use of at least 20 / last 28 days. **4)** Participants must express a desire to reduce cannabis use or quit. **5)** Participants must have a positive UDT for cannabis during their enrollment visit (confirming they are regular users). **6)** The investigative team must believe each participant is a good study-candidate.

**Exclusion Criteria: 1)** Participants must not be pregnant or breastfeeding. **2)** Participants must not meet moderate or severe use disorder of any other substance with the exception of Tobacco Use Disorder. **3)** Participants must not be regularly taking any medications that have central nervous system effects that have changed in the past 6-weeks. **4)** Participants must not have a history of/or current psychotic disorder or bipolar disorder. **5)** Participants must not have any other Axis I condition requiring current treatment. **6)** Participants must not have a history of dementia or other cognitive impairment. **7)** Participants must not have active suicidal ideation or a suicide attempt within the past 180 days. **8)** Participants must not have any contraindications to receiving rTMS or MRI (e.g. metal implanted above the head, history of seizure, any known brain lesion). **9)** Participants must not have any unstable general medical conditions.

**DATA MANAGEMENT AND STATISTICAL ANALYSIS:** Behavioral data will be managed using REDCap and all data entry will take place directly in REDCap. We will use e-consents through Adobe sign, and these documents will be uploaded into REDCap. There will however be emergency paper backups of the database should it be unavailable for any reason. If data is collected on paper, the information will be immediately transferred to the REDCap database, and the paper record will be safe-shredded. Video and Audio recordings will be uploaded to Stanford Medicine Box, as will be backup copies of MRI files.

Statistical Analysis: The primary outcomes for this study are generally qualitative in nature and will serve as pilot data to power a larger trial if indicated. We will subsequently not perform formal hypothesis testing. We will, however, generate proportions of success for retention (Aim1) and fMRI target generation of our ROC-task for both vmPFC and L-DLPFC (Aim2). We will further calculate effect sizes for clinical, behavioral, and fMRI outcomes (Aim3), and compare them qualitatively to the results of our phase-2 trial (where we have complete data for N=28 participants who received anatomically targeted L-DLPFC stimulation and 23 participants who received sham stimulation)—assuming we find this paradigm to be feasible, and our functional-targeting development successful, we believe we will have a sufficient sample size to compare effect sizes between the two open-label conditions, our prior active condition, and our prior sham condition—acknowledging that the comparison will be imperfect with this trial being open-label, and the previous trial being double-blind. All statistical analysis will be conducted using SAS/STAT version 9.4 (SAS Institute Inc. 2015. SAS® 9.4 Statements: Reference, Fourth Edition. Cary, NC: SAS Institute Inc.).

Missing Data and Attrition. Missing data in longitudinal studies can be a problematic feature but can be mitigated through study design considerations. In order to minimize missing data and study attrition, study simplification and enhanced communication between study staff and participants will be emphasized. We will make every effort to prevent attrition (e.g., phone/text visit reminders, participation compensation, reinforcing adherence to the study protocol at each visit). In addition, in keeping with the Intent to Treat Principle, we will make every effort to continue assessments for the entire course of randomized treatment, even among those who fail to adhere to randomized assignment or stop participating in the study assigned intervention.

Sample Size Justification: The primary focus of this study is to show evidence, with sufficient strength, that our proposed treatment paradigm is feasible, that we can generate functionally derived rTMS targets, and that our new, refined, protocol has suggestions of improved efficacy relative to our lower burden/complexity paradigm. We reasoned that we must be able to retain approximately 60% of the study sample to design a reasonable Phase-3 trial with an expanded number of treatments (10% lower retention rate than our Phase-2 trial), and that we must be able to generate functional targets for 2/3rds of participants to justify the increased complexity of the paradigm. Finally, assuming a 60% retention rate, we reasoned we would need at least 9-participants per cell to generate a meaningful effect size (Aim3, weeks of abstinence and days per week of cannabis use in the 12-weeks following the delivery of 14-study treatments) with which to judge whether the new paradigm is an improvement relative to the old paradigm.

**Relapse, Drop-Out and Clinical Deterioration:** Every effort will be made to re-engage participants who miss appointments. Clinical deterioration, such as exacerbation of psychiatric or substance use disorder, will be assessed on a case-by-case basis by one of the study clinicians, most often [name] (a licensed and board-certified psychiatrist) and appropriate referral will be made. Participants will be considered dropouts if they do not come back to treatment after receiving three phone calls.

**Strategies to ensure a robust and unbiased approach:** The proposed study will achieve robust and unbiased results via several design features including: explicit inclusion/exclusion criteria; randomization of treatment condition; use of validated laboratory and interview/self-report measures and methods; explicit hypotheses and corresponding planned statistical analyses; power estimates; planned handling of retention/attrition and missing data; and careful consideration of potential confounds. All experimental details are reported in a detailed and fully transparent manner to support replication.

**Consideration of gender as a biological variable:** Though this trial is not powered to detect gender differences, we will perform our analysis using gender as a potential covariate, and should there be a potential gender difference found, we will be able to use that data to power a larger trial.

#### **E. PROTECTION OF HUMAN SUBJECTS**

a. Participant description and compensation

[figure not shown]
## **Targeted/Planned Enrollment Table**

Total Planned Enrollment 30 (Randomized)

TARGETED/PLANNED ENROLLMENT: Number of Subjects				
	Sex/Gender			
Ethnic Category	Females	Males	Total	
Hispanic or Latino	2	3	5	
Not Hispanic or Latino	9	16	25	
Ethnic Category: Total of All Subjects*	30			
Racial Categories				
American Indian/Alaska Native	0	0	0	
Asian	1	1	2	
Native Hawaiian or Other Pacific Islander	1	1	2	
Black or African American	3	4	7	
White	4	9	13	
Other / More than one race	2	4	6	
Racial Categories: Total of All Subjects*	11	19	30	

We will attempt to recruit all potential participants from the community. We will not exclude anyone based on gender, ethnicity, or race. The above estimated enrollment numbers are based on our experience with this clinical population as well as our recently completed phase-2 trial.

**Compensation and Retention:** Participants will be compensated based upon attending visits as well as given additional compensation using a Prize-Based Contingency Management (PB-CM) paradigm. Participants who attend all visits as scheduled will receive for visit attendance, and up to an additional for PB-CM (see below for a further description of each type of compensation).

Prize-Based Contingency Management (PB-CM) will be used to reinforce visit attendance. In PB-CM
participants pick a pre-specified number of numbered-chips out of a bowl. Each number corresponds to a
dollar amount—in this case 250 chips will be used (230 chips will be worth \$ 18 chips will be worth \$ one
chip will be worth \$ and one chip will be worth \$ Participants will be given a chip pick for attending the
initial MRI visit, and then every other visit that is attended on time and without rescheduling, the number of
chips will escalate by 1. If a participant misses a scheduled visit or attends more than 10-minutes late the
number of chip-picks reset to 1 and again escalate by a chip-pick every-other visit. The amount of
compensation based on PB-CM, will by definition vary to some degree between participants, but fall within a
predictable range. The average value of a chip is (230*\$\frac{1}{2} + 18*\$\frac{1}{2} + 1*\$\frac{1}{2} + 1*\$
\$ per chip). Using the escalation paradigm described above, participants who attend all visits as scheduled
will receive 144 chip picks. Participants who attend all visits as scheduled will subsequently be compensated a
minimum of \$ a mean / median (since chips are picked at random) of 144*\$ = \$ , and we will
cap PB-CM total compensation at \$ We used this strategy successfully in our prior Phase-2 trial (with
fewer visits) and found the mean value of each chip pick was \$
The total estimated direct time commitment for the study is approximately 38.5 hours (not accounting for travel
time), and so participants receiving the expected amount of PB-CM compensation will be compensated
approximately \$ per hour—when including travel time and cost of travel we believe this is a reasonable
amount of compensation and is not likely to be coercively high.

# b. Sources of Materials

## **Assessments:**

# Data collection:

# **Research Procedures Table**

	Screening Visit	Baseline fMRI Visit	rTMS Visits	Post- Tx fMRI Visit	Follow- up Visits		
Screening and Enrollment Eligibility							
Quick Structured Interview for the DSM-5 (Quick-SCID-5)  , Medical, Surgical, Social, Family, and Medication History	Х						
Brief Counseling for Marijuana Dependance Questionairres  : A series of measures used to complete the personal feedback form of the Motivational Enhancement Therapy behavioral intervention including the Marijuana Problem Scale, the Reasons for Quitting Questionnaire and the Self-Efficacy Questionnaire	х						
Urine Pregnancy Test (bHCG) for participants of childbearing potential	Х						
Study Procedures:							
MRI-Procedures:		Х		Х			
Repetitive Transcranial Magnetic Stimulation (rTMS) study-treatments			Х				
Brief Counseling for Marijuana Dependance sessions:		Х	~5 & ~10				
Clinical Substance Use Measures:							
Craving Scale (CS)  : Validated brief measure of sub-acute craving (past 24-hours), that has predicted future use of	Х	Х	Х	Х	Х		

substance in Alcohol, stimulants, and opioids.					
The Marijuana Craving Questionnaire (MCQ)  : Validated measure of immediate cannabis craving, for use at MRI visits.		х	Х	Х	
Time Line Follow Back (TLFB)  : Calendar-based instrument designed to assess substance use.	Х	х	Х	Х	Х
Diagnostic criteria for Cannabis Use Disorder from the Structured Interview for the DSM-5  , and additional quantifying questions via the Repeatable Clinician-Administered Diagnostic Interview for Substance Use Disorders (CADiSUDS)—recently developed by our team. *With participant permission we may videotape administrations of the CADiSUDS for QA, training, and dissemination purposes.	X	X	#8 only	X	×
Urine Drug Testing with creatinine corrected cannabinoid levels	Х	Х	#16 only	Х	Х
Cannabis Withdrawal Scale (CWS)  : Validated questionnaire that measures symptoms of cannabis withdrawal.	Х	х	Х	Х	Х
Participant Burden, Quality of Life, and Function / Functional In	nprovement:				•
Marijuana Problem Scale (MPS) 	Х			Х	Х
Q-LES-Q-SF  : Brief measure of quality of life and the Work Productivity and Activity Impairment (WPAI-SF) scale 	X	X	Weekly	Х	Х
Perceived Research Burden Assessment 			Final Visit		Х
Cognitive Tasks and Relevant Covarying Symptoms:					
Delayed Discounting Task: Participants choose between receiving hypothetical money / cannabis immediately or more money / cannabis if they wait longer. Determine whether participants favor smaller immediate rewards or larger delayed rewards.		х	#8 only	Х	x
Behavioral GoGo-NoGo Task / n-back / CPT: Behavioral version of the fMRI tasks described above. We may collect these, time permitting		х	#8 only	Х	х
We will measure relevant covarying symptoms including sleep  , depression  , ADHD, impulsivity  and anxiety  . If there is question as to whether there is sufficient symptomatology in depression or anxiety to require separate treatment, we may perform the more extensive clinician rated measures  .	Х	х	#8 only	Х	х

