In this proposed pilot trial, we subsequently hope to build on our promising results suggesting that a relatively low dose of simply-targeted L-DLPFC applied rTMS may help treatment seeking participants with CUD reduce their cannabis use—by testing the feasibility and preliminary efficacy of three refinements. The three refinements include: a) increasing the number of study-treatments delivered from 20 to 36; b) testing the ability of an fMRI task we developed (based on prior similar tasks) to generate functional rTMS targets (which we will use for more precise targeting at two established treatment sites); and c) the preliminary comparative efficacy of applying rTMS to a second commonly targeted cortical site/circuit which may have efficacy in a different sub-type of addictions. In order to do so, we plan on recruiting N=30 treatment-interested participants with ≥moderate CUD and randomizing them to receive 36-study-treatments of rTMS applied to either the L-DLPFC or vmPFC, delivered over 6-9 weeks (two-study-treatments per visit, 18-study-treatment visits, two or three visits per week), and following them for 6-weeks. We will perform fMRI before and after study-treatment and attempt to use the pre-treatment fMRI to derive a functional rTMS target.

Aim-1 will determine the feasibility and acceptability of delivering our expanded study-treatment paradigm. We

Aim-1 will determine the feasibility and acceptability of delivering our expanded study-treatment paradigm. We will quantify acceptibility, and consider our paradigm feasible if we retain >60% of our randomized sample. Aim-2 will determine if our fMRI task is able to reliably generate a functional rTMS treatment target within the broader L-DLPFC and vmPFC structures. We will consider our task effective if the generated center of mass falls within the broader structures that we have targeted in >2/3rds of scans. We will use anatomically-derived targets as backup should one or more participants not have a clear fMRI center of mass to target.

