The findings from our preliminary work as well as therapeutic studies applying rTMS to the DLPFC of other addictive disorders suggest therapeutic promise for CUD, though the need for a treatment-paradigm that differs from daily applications. Both data and clinical experience suggest it is possible to get a therapeutic effect from rTMS even if treatments are delivered less frequently then daily, and so we completed a Phase 2 trial that randomized N=72 (mean age 30.2±9.9SD, 37.5% women) treatment-interested participants with ≥moderate CUD (8.5±1.5SD CUD criteria, 6.6±1.1SD days per week of use, 4.3±3.3SD use sessions per day) to active or sham rTMS, where study-treatments were delivered twice weekly for five-weeks. On each treatment-visit we delivered two study-treatments in the presence of cannabis-cues, separated by 30-minutes, for a total of 20 sessions of rTMS. We also delivered a three-session Motivational Enhancement Therapy (MET) behavioral intervention. We reasoned that this lower participant burden paradigm maximized feasibility while delivering the minimum amount of rTMS needed to produce a therapeutic effect. In order to maximize future potential

translation we used the original rTMS for depression treatment paradigm (10Hz, scalp-based measurement), and used a low-intensity behavioral platform. We found that the paradigm was feasible with 51 of the 72 participants completing study-treatment (28 of 37 active, 23 of 35 sham), and that those treated with active rTMS had more numeric weeks of abstinence beginning after the delivery of 16-study treatments (14.86% active; 9.05% sham; RR 1.64 [0.97,2.79]; missing data coded as non-abstinent) and numerically fewer days per week of cannabis use in the final two weeks of follow-up (3.67±3.09SD and 3.59±2.75SD-active;

 $4.67\pm2.50$ SD and  $5.00\pm2.45$ SD-sham; Cohen's D at week 4 = 0.54; among completers) than those treated with sham-rTMS.

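### Perceived burden is first scored at the final rTMS visit and no exit assessment is described, so Aim-1 acceptability would rest mainly on completers

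*Combined protocol and SAP*

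**What the plan says.** Specific Aims states that Aim 1 will "determine the feasibility and acceptability of delivering our expanded study-treatment paradigm". The two halves of that aim are treated differently. For feasibility there is a rule: the team will "consider our paradigm feasible if we retain >60% of our randomized sample". For acceptability the text says only that the team "will quantify acceptibility", with a literature citation and no instrument, score or analysis population. The Statistical Analysis paragraph gives one Aim-1 quantity, the proportion retained.

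In the Research Procedures Table, the one scale of participant burden is the "Perceived Research Burden Assessment". Its row is marked at the final rTMS visit and at the follow-up visits. It is blank at screening, at both fMRI visits and at every earlier rTMS visit. Other rows are collected mid-course: at each rTMS visit, weekly, at visit 8 or at visit 16.

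The Follow-up section times its visits at one, two, four and six weeks from completion of study treatment. The paragraph on relapse and drop-out says: "Participants will be considered dropouts if they do not come back to treatment after receiving three phone calls". No early-termination visit or exit questionnaire is described. The Missing Data and Attrition paragraph states a general intention to go on assessing people who stop the assigned intervention.

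**The concern.** The trial asks whether participants will accept a longer and heavier course: 18 treatment visits and about 38.5 hours in total, per the compensation section. People who find it too heavy are likely to be among those who leave. If burden is first asked about at the end of the course, their view is the one most likely to be absent, and the loss grows with dropout.

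The acceptability result is meant to help decide whether this paradigm goes into a larger trial. A favourable score drawn largely from those who stayed would say little about the course as experienced by everyone randomised, and it cannot be recovered once people have left.

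**Working it through.** **Inputs**
- Randomised: 30, as two arms of 15 (Targeted/Planned Enrollment Table, "Total Planned Enrollment 30 (Randomized"; design figure text).
- Planning retention: 60% (Sample Size Justification, "assuming a 60% retention rate, we reasoned we would need at least 9-participants per cell").
- Feasibility rule: more than 60% retained (Specific Aims).
- Phase-2 completion: 51 of 72 overall, 28 of 37 on active rTMS (Background and Significance).
- Share of completers who find the burden acceptable: not in the documents. 80% is assumed for illustration.

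**Plan's own figure.** 15 × 0.60 = 9 per cell, which reproduces the stated 9. Over two arms, 18 are retained and 30 − 18 = 12 are lost.

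**How many could lack a burden score if only completers supply one**
- Phase-2 overall rate: 51/72 = 70.8%; 30 × 0.708 = 21.25, so about 21 complete and 9 are missing (30%).
- Phase-2 active-arm rate: 28/37 = 75.7%; 30 × 0.757 = 22.7, so about 23 complete and 7 are missing (23%).
- Smallest number that meets the feasibility rule: 18/30 = 60% is not more than 60%; 19/30 = 63.3% is. So 19 complete and 11 are missing (37%).
- Planning rate: 18 complete and 12 are missing (40%).

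**What completers' scores can say about all 30.** Let c be the completers, m = 30 − c the missing, and a the acceptable share among completers. The rate among all randomised lies between a·c/30 (no missing person found it acceptable) and (a·c + m)/30 (every missing person did). With a = 0.80:

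| Completers | Missing | Lower bound | Upper bound |
|---|---|---|---|
| 23 | 7 | 18.4/30 = 61% | 25.4/30 = 85% |
| 21 | 9 | 16.8/30 = 56% | 25.8/30 = 86% |
| 19 | 11 | 15.2/30 = 51% | 26.2/30 = 87% |
| 18 | 12 | 14.4/30 = 48% | 26.4/30 = 88% |

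The width is m/30 whatever value a takes, so the uncertainty does not depend on the assumed 80%. With 18 completers, a = 0.70 gives 42% to 82% and a = 0.90 gives 54% to 94%.

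**The case against.** A reader might infer that burden is measured only in people who did not drop out, and that anyone who stops early is never asked. The documents do not support that. The Missing Data and Attrition paragraph intends to continue assessments after someone stops the intervention, and the scale is also scheduled at follow-up, so a person who stops rTMS but stays in contact could be scored. The final-visit entry could even be read as each participant's own last visit. These points rule out the word only, but the safeguard is weak. The intention is general and covers the course of treatment, during which the scale is not due until the last visit. Follow-up is timed from treatment completion, with no stated schedule for early leavers. Someone who leaves without notice does not attend a visit known to be the last.

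The link to Aim 1 is also inferred. No passage designates this scale as the acceptability measure, and the aim's citation differs from the scale's. That stands. If the scale is not the measure, however, Aim 1 has no scheduled acceptability measure at all, and the plan still needs a change.

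Acceptability is not among the listed primary or secondary outcomes, has no cut-off, and enters no hypothesis test. Retention counts everyone randomised, and adverse events are assessed at each visit. This limits the consequence. But attendance is reinforced by escalating prize draws that reset after a missed or late visit, so retention partly reflects the incentive, and adverse events measure tolerability. Neither measures burden.

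Finally, losing 12 of 30 fails the rule in Specific Aims, so it is not a scenario that the plan accepts there, although the Sample Size Justification speaks of approximately 60%. That is why the 19-retained case matters: the criterion is met and 11 scores may still be absent.

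**Conclusion.** The concern holds in limited form. As scheduled, burden scores will come mainly from completers, because nothing is collected before the final rTMS visit and no exit assessment is described.

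On the document's own retention figures, between about 7 and 12 of 30 could lack a score: about 9 at the overall Phase-2 rate, and up to 11 with the feasibility criterion met. These counts assume that no early leaver is scored, so they are upper limits for each retention level.

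Upward bias is the likely direction, but nothing in the documents establishes it. A reader might want to quote a specific amount of bias. That needs a figure for how early leavers rate the burden, and the documents give none, so only the bounds above are justified. This is an inexpensive improvement to a descriptive result in a pilot; it does not undermine the retention criterion.

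**What to change.** - Name the scale in Aim 1 and in the Statistical Analysis paragraph as the acceptability measure.
- Add it at rTMS visit 8, where diagnostic, cognitive and symptom measures are already taken.
- Add it at discontinuation, together with the reason for leaving, attempted during the re-engagement calls already planned.
- Report the number of respondents out of all 30 randomised, by time point, and separately for completers and early leavers. Do not carry a visit-8 score forward as an end-of-course score, since the two describe different amounts of exposure.

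The cost is one short questionnaire at an existing visit and an existing phone contact: a few minutes of participant time and no new visits. It will not close the gap fully. Dropouts are by definition people who did not return after three calls, so some will not answer, and those who leave before visit 8 are the most likely to remain missing. Reporting the denominator makes that loss visible.
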